#### d Inclusion Criteria

Participants will be included if, by self-report, they are Asian American women who identify as Chinese or Korean; are caregivers of PLAD; can read and write English, Mandarin Chinese or Korean; and have access to the Internet through computers or mobile devices. Participants must be providing assistance for the PLAD in the early-middle stage of illness (Clinical Dementia Rating of  $\geq$  1) for whom there is no plan for institutionalization in six months. Caregivers may or may not reside with their care recipient.

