#### 3 Study Background

Provide the rationale and the scientific or scholarly background for the proposed activity, based on existing literature (or clinical knowledge). Describe the gaps in current knowledge that the project is intended to address.

PLAD spend most of the course of their illness in the community and receive most of their care from informal (usually family) caregivers. Currently, about 15 million adults, mainly women, annually provide 17.9 billion hours of family care for community-dwelling persons living with Alzheimer's and other illnesses. The situation is worse for **AACA**. Under-detection of cognitive impairment among Asian Americans remains prevalent, and their cultural stigma produces suboptimal dementia management, placing them at a greater risk than Whites. Although Asian Americans include highly diverse sub-groups, all Asian Americans across the sub-groups share many common characteristics, one of which is "filial piety," the belief that family members are in charge of caregiving roles. Mainly due to this cultural belief, 42 percent of Asian Americans reportedly provide care to an older adult while 22 percent of the general population provides care to an older adult.

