Instruments. The instruments to measure caregivers' health outcomes (primary outcomes; Hypothesis 1) include: (a) Multidimensional Caregiver Strain Index, Perceived Stress Scale, Acculturation Stress Scale (ASS), 148 and Social Readjustment Rating Scale (SRRS)  (to measure stress); (b) the Women's Symptom Index (to measure physical and psychological symptoms); and (c) EQ-5D-5L(to measure the quality of life). The instruments to measure care recipients' health outcomes (primary outcomes; Hypothesis 1) will include: (a) Informant Questionnaire on Cognitive Decline in the Elderly (IQCODE)(to measure the cognitive status of care recipients); (b) Lawton ADL/IADL Scale (to measure PLAD's activities of daily life); (c) Revised Memory and Behavior Problem Checklist (to measure behavioral and psychological symptoms of care recipients); (d) Neuropsychological Inventory Questionnaire (to measure care recipients' mood status); and (e) Quality of Life Scale in Alzheimer's Disease (to measure care recipients' quality of life). The instruments to measure caregiving experience (secondary outcomes; Hypothesis 2) will include: (a) Caregiver Activity Survey (to measure caregiving activity); (b) Ways of Coping Scale (to measure coping); (b) Pearlin Mastery, Loss, and Competence Scale (to measure caregivers' mastery of caregiving competence); and (c) Caregiver Assessment of Behavioral Skill Scale (to measure caregiving skills). 163 The theory-based variables (attitudes, self-efficacy, perceived barriers, & social influences; Hypothesis 3) will be measured using the modified Questions on Attitudes, Subjective Norm, Perceived Behavioral Control, and Behavioral Intention (QASPB). 164 Covariates that will be considered in determining the effect of TACAD on outcome variables include caregivers' sociodemographic characteristics and caregiving history (e.g., socioeconomic status, PLAD information, length of caregiving, co-residence with recipient). The reliability and validity of all the instruments have been established among Asian Americans. Cronbach's alpha of the instruments ranged from .70 to .96 among Asian Americans. Because no existing instruments have culture-specific measures, we will add open ended questions to all the measures to explore culture specific aspects that are missing in the specific measures. The same questionnaire will be used at the three time points except the questions on sociodemographic characteristics and caregiving history (e.g., socioeconomic status, PLAD information, length of caregiving, co-residence with recipient). The questions on sociodemographic characteristics and caregiving history (e.g., socioeconomic status, PLAD information, length of caregiving, co-residence with recipient) will be asked only at the pre-test. This has been clarified on p. 10.

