#### e Exclusion Criteria

Describe the specific criteria that will be used to decide who will be EXCLUDED from the research. Define technical terms in lay language, as applicable.

Those who used the AA website previously and/or participated in other studies related to AD will be excluded. Men are excluded because the intervention was designed for Asian American women who are family caregivers of persons living with Alzheimer's Disease.

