## 17 Identification and/or Screening Procedures

Describe the identification and/or screening procedures below.

When potential participants visit the project website after seeing the study announcements posted on online and offline communities/groups, they will be provided with the information sheet (consent form) and asked to give their consent by clicking the "I agree to participate" button. Then, when they agree, they will be verified against the inclusion and exclusion criteria (see the above) by server-side programs. When they meet the criteria, they will be asked about their sub-ethnicity. Then, the potential participants will be divided into Chinese and Korean, and randomized into two groups using an automated random number generator via the project website.

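### Eligibility rules out planned institutionalization but does not require that the care recipient lives in the community now

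*Combined protocol and SAP*

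**What the plan says.** The Inclusion Criteria (item d) hold the whole care-setting rule. "Participants must be providing assistance for the PLAD in the early-middle stage of illness", with a Clinical Dementia Rating of at least 1, and the recipient must be one "for whom there is no plan for institutionalization in six months". The next sentence adds: "Caregivers may or may not reside with their care recipient". No minimum hours of care and no primary-caregiver role are set.

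The Exclusion Criteria (item e) do not mention where the recipient lives: "Those who used the AA website previously and/or participated in other studies related to AD will be excluded", and men are excluded.

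Eligibility rests on the woman's own report; the inclusion paragraph opens "if, by self-report, they are Asian American women who identify as Chinese or Korean". Section 17 describes the check: after consent, "they will be verified against the inclusion and exclusion criteria (see the above) by server-side programs". The Phase 2 (Aim 2) procedures then randomise eligible women automatically through the website.

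The Study Background (section 3) describes the setting the trial has in mind: "PLAD spend most of the course of their illness in the community", cared for mostly by family.

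On outcomes, the Instruments paragraph under Phase 2 (Aim 2) reads "The instruments to measure care recipients' health outcomes (primary outcomes; Hypothesis 1) will include", followed by measures that include daily activities, behaviour, mood and quality of life. Caregiving activity and skills are secondary outcomes under Hypothesis 2. Co-residence and information about the recipient are examples of covariates; residence in a facility is not named.

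**The concern.** The criterion excludes a placement that is planned and is silent on one that has already happened. A woman whose mother moved into a nursing home last year can truthfully say that no institutionalization is planned. Read literally, the rule excludes the recipient who may enter a facility within six months and admits the one who is already there. That defeats its evident purpose.

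The wording carries more weight here than in a trial with a screening visit, because the documents describe no person who would judge eligibility between self-report and automatic randomisation.

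At stake are the outcomes that TACAD can change only through the enrolled woman's day-to-day care: the recipient's daily activities, behaviour, mood and quality of life, and her own caregiving activity and skills. If others provide much of the daily care, the programme has less room to move these measures, and a real effect would be harder to see in a trial of 60.

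**Working it through.** **Step 1. Does any other criterion close the gap?**

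- *Providing assistance.* This narrows the group. With no minimum involvement set, though, a daughter who visits and helps a parent in a facility still provides assistance.
- *Early-middle stage.* This also narrows it. But the stage is tied to a Clinical Dementia Rating of at least 1 with no upper limit, so advanced disease is not excluded by number.
- *Co-residence.* Expressly not required. As a covariate it separates women who live with the recipient from those who do not, but the second group mixes recipients at home with recipients in facilities.
- *Exclusions.* Prior use of the AA website, other AD studies, and men. Nothing on residence.

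The gap is narrowed but stays open.

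**Step 2. The plan's own power figure.** Section 15 gives 105 per group for 80% power, type I error 0.00625 and a difference of 0.5. The SD is not stated; I take it as 1. The normal approximation is n = 2(z₁₋α/₂ + z₀.₈)²/d² = 2(2.734 + 0.842)²/0.25 ≈ 102.3, so 103 per group. The noncentral-t calculation gives 105 (power 0.804). The plan's figure reproduces, so 0.5 can be read as a standardized difference.

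**Step 3. Illustration of dilution.** Inputs from the plan: d = 0.5, 30 per arm (section 15), two-sided .05 (section 5). Assumptions that are not in the plan: a share f of recipients already in a facility, no effect on the outcome in that share, SD 1 throughout, and a simple two-sample t test.

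Diluted effect = 0.5 × (1 − f). Power is from the noncentral t with 58 degrees of freedom, noncentrality = effect × √(30/2), critical value 2.002.

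| f | Women of 60 | Effect | Noncentrality | Power |
|---|---|---|---|---|
| 0 | 0 | 0.50 | 1.936 | 47.8% |
| 5% | 3 | 0.475 | 1.840 | 44.0% |
| 10% | 6 | 0.45 | 1.743 | 40.3% |
| 20% | 12 | 0.40 | 1.549 | 33.2% |
| 30% | 18 | 0.35 | 1.356 | 26.6% |

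**Step 4. Chance imbalance.** Suppose 12 of 60 recipients were in facilities and allocation were a simple 30/30 split (ignoring the sub-ethnic strata). The number in one arm is then hypergeometric with mean 6. The arms differ by 4 or more such women unless that number is 5, 6 or 7, which has a probability of about 33%. This is noise in a single trial, not systematic bias.

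**The case against.** The strongest reply is that the absence of a plan for institutionalization naturally presupposes a recipient who is not yet institutionalized, and that whoever builds the screen will read it that way. The screening items are not in the documents. Section 21 sends participants to Qualtrics for screening, and section 32 mentions detailed screening questions, so current residence may be asked. This stands in part. A reader might infer that such women do pass the screen; the documents do not show that. They support only a conditional statement: such women can be randomised if the screen follows the criteria as written, and checking those criteria is what section 17 says it does.

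A second tempting inference is that facility staff, not the enrolled woman, determine the recipient outcomes. The documents say nothing about facility staff. A weaker effect in that setting is plausible but is an inference, and zero effect is the worst case. Caregiver stress, symptoms and quality of life are also primary and would be less affected, as would coping and the Hypothesis 3 variables.

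A third is that the comparison would be biased. It would not: randomisation leaves dilution and added variance. The hypotheses also adjust for background factors, and the covariate list is open-ended, so residence could be included; it is simply not named.

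Finally, the shares in the table have no source, the planned analysis is a mixed model over three time points rather than a t test, and the low starting power reflects a sample size that section 15 openly accepts for an exploratory pilot. All of this limits what the table can show. None of it removes the gap in the wording.

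**Conclusion.** The point holds as a gap between the written criterion and its evident purpose. Current community residence is not required anywhere in the eligibility criteria, co-residence is not required, and the described screen is automatic and based on self-report. A woman whose relative is already in a facility can meet every written criterion.

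The consequence is possible dilution and noise in the care-recipient outcomes and in caregiving activity and skills. Its size cannot be known from the documents. Under the stated assumptions, shares of 10% to 30% take power from 48% to between 40% and 27%; at 5% the loss is about 4 points (47.8% to 44.0%). These figures show what could happen and are not an estimate of what will.

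**What to change.** Reword the criterion along these lines: *the PLAD currently lives in the community (not in a nursing home or other long-term institution) and there is no plan for institutionalization in six months.* The sponsor should state how assisted living is classed, because a relative may still give substantial help there and the present text does not settle it.

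Ask current residence as its own screening item, before the question about plans and before randomisation. Record the answer at baseline and name it as a covariate.

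The cost is one clause, one screening question and one named covariate. The downside is that a few screened women become ineligible.

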#### e Exclusion Criteria

Describe the specific criteria that will be used to decide who will be EXCLUDED from the research. Define technical terms in lay language, as applicable.

Those who used the AA website previously and/or participated in other studies related to AD will be excluded. Men are excluded because the intervention was designed for Asian American women who are family caregivers of persons living with Alzheimer's Disease.

## **14** Total Sample Size

Enter the total target sample size below.

60

## **15** Sample size rationale

Describe your sample size rational below.

To test Hypotheses 1 to 3 (Aim 2), with 80% power and a type I error rate equal to 0.00625 to account for 9 outcome measures modeled within two hypotheses, group sample sizes of 105 each will have enough power to detect a difference of 0.5 between group means overall in the follow-up period. However, considering the proposed study period, limited budget, and the inherent explorative nature of the study, we will include only 60 (30 per group) women; 30 will be adequate for a pilot intervention study.

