## **2** Research Hypotheses

Please describe the research aims and hypotheses in the box below. To input text, click in the box below and start typing.

Note: Procedures will be explained in a separate section below.

The purpose of the proposed study is to preliminarily evaluate a technology-based information and coaching/support program, TACAD (Technology-based Information and Coaching/Support Program for Asian American women who are family caregivers of persons living with Alzheimer's Disease), in improving health outcomes of Asian American women who are family caregivers of persons living with Alzheimer's disease (AACA) and their care recipients. The **specific aims** of the study are to:

- Aim 1. Qualitatively evaluate TACAD through an expert review and a usability test.
- **Aim 2**. Quantitatively evaluate the preliminary efficacy of TACAD in improving health outcomes of AACA and their care recipients.
- -Hypothesis 1. After controlling for background and health/disease factors, the intervention group (AACA who use TACAD and the Alzheimer's Association [AA] website) will show significantly greater improvements than the

active control group (AACA who use only the AA website) in their health outcomes (stress, physical and psychological symptoms, and quality of life) and their care recipients' health outcomes (activities of daily living, behavioral and psychological symptoms, mood status, and quality of life) from baseline (pre-test) to Time Points 1 (post 1 month) and 2 (post 3 months).

- -Hypothesis 2. After controlling for background and health/disease factors, the intervention group will show significantly greater improvements than the control group in caregiving experience (caregiving activity, coping, caregiving competence, and caregiving skills) from baseline to Time Points 1 and 2.
- -Hypothesis 3. After controlling for background and health/disease factors, the intervention group will show significantly greater improvements than the control group in theory-based variables (attitudes, self-efficacy, perceived barriers, and social influences related to caregiving of PLAD) from baseline to Time Points 1 and 2.

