## 5 Data Analysis

Describe the data analysis plan, including any statistical procedures or power analysis.

The data will be randomly assigned with serial ID numbers. All tests will be assumed two-sided and an alpha level of .05 will be used. SAS 9.4 will be used for data processing and all statistical analyses. Missing data will be handled by multiple imputations of dependent values. 101–103 Analyses just of complete data will be conducted and comparisons of groups with and without missing data will be made. In addition, sensitivity analyses of complete data will be conducted and compared imputed data analysis. An **intent-to-treat** analysis will be employed. For **Hypotheses 1 to 3**, differences in continuous outcome measures over time will be examined using **linear mixed-effects modeling.** In particular, we will fit mixed effects models to each continuous outcome measure. We will use random intercepts as well as explore random slopes to represent subject level variability. Fixed-effects corresponding to group, time and group x time interaction will be included in the model. A significant group x time interaction will indicate substantial differences in the groups over time. Restricted maximum likelihood method will be used for estimation, and the most appropriate covariance structure will be examined.

Since Data and Safety Monitoring Boards (DSMBs) are required only for phase III clinical trials (NOT-OD-00-038.html), we do not include a DSMB for this intervention study. For the proposed intervention study, we have

the following data safety monitoring plan (DSMP). First, to manage and protect the data collected, only summary data will be openly accessible to funding agency or will appear in publications. Research participants will be informed that they are free to decline to answer any questions they do not wish to answer or to stop participating in the project at any time. When a participant withdraws from participation, the data that they have provided will be immediately removed. Also, the data will have no identifying information to link a subject to the data.

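### Section 15 corrects alpha for nine unlisted outcomes with a divisor of eight, and section 5 neither applies that correction nor disclaims it

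*Combined protocol and SAP*

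**What the plan says.** Section 15 (Sample size rationale) bases its calculation on "a type I error rate equal to 0.00625 to account for 9 outcome measures modeled within two hypotheses". The sentence begins by saying that it serves Hypotheses 1 to 3. With 80% power and a difference of 0.5, it arrives at 105 per group. The next sentence sets that number aside on grounds of time, budget and the exploratory character of the study, and enrols 60 (30 per group).

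Section 5 (Data Analysis) says "All tests will be assumed two-sided and an alpha level of .05 will be used". It continues "we will fit mixed effects models to each continuous outcome measure", and gives the reading rule "A significant group x time interaction will indicate substantial differences in the groups over time". It does not mention 0.00625, nine outcomes or any multiplicity procedure.

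Section 2 (Research Hypotheses) names the outcomes as constructs:
- **Hypothesis 1, caregiver:** stress, symptoms and quality of life.
- **Hypothesis 1, care recipient:** "activities of daily living, behavioral and psychological symptoms, mood status, and quality of life".
- **Hypothesis 2:** "caregiving activity, coping, caregiving competence, and caregiving skills".
- **Hypothesis 3:** four theory-based variables.

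For Hypotheses 2 and 3 it predicts that "the intervention group will show significantly greater improvements than the control group in" these outcomes, and Hypothesis 1 is worded to the same effect. The Instruments paragraph of the Procedure Description labels 11 instruments as primary for Hypothesis 1. One of them is a cognition measure (IQCODE), a construct that Hypothesis 1 in section 2 does not name.

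**The concern.** Two things disagree. Within section 15, the divisor (eight), the stated count (nine) and the number of hypotheses (three, then two) do not fit together, and without a list nobody can check which is right. Between sections, the sizing assumes a corrected significance level that the analysis plan does not carry forward.

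The second is the one with consequences. Suppose a primary outcome gives a group-by-time p-value of 0.02. That is significant under section 5 and not under the level in section 15. The plan does not say which applies, so the rule could end up being chosen after the results are known. With many primary outcomes each tested at .05, an isolated significant result is also weak evidence that the program works.

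**Working it through.** **1. Reproducing the 105.** Inputs from section 15: alpha 0.00625, power 80%, difference 0.5. Two-sidedness comes from section 5. The SD is not stated, so SD = 1 (a standardized difference) is assumed. The two-sample t test (noncentral t) gives 105 per group, power 0.804. The normal approximation gives 103. The plan's figure therefore follows from 0.00625, and that was the level used.

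**2. The divisor.**
- 0.05/8 = 0.00625 exactly.
- 0.05/9 = 0.00556.
- A Sidak correction does not explain it: 1 − 0.95^(1/8) = 0.00639 and 1 − 0.95^(1/9) = 0.00568.
- At 0.00556 the same t test needs 107 per group; at 105 per group its power is 0.793.
- At the .05 of section 5 it needs 64 per group.

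**3. Where eight or nine might come from.**

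| Basis | H1 | H2 | H3 |
|---|---|---|---|
| Constructs, section 2 | 7 (8 with physical and psychological symptoms split) | 4 | 4 |
| Constructs, adding cognition from Instruments | 8 (9 with symptoms split) | 4 | 4 |
| Instruments | 6 + 5 = 11 | 4 | 1 (covering four variables) |

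Eight can be reached from H1 alone (section 2 with symptoms split, or unsplit with cognition added) or from H2 + H3 (4 + 4). Nine can be reached from H1 alone (symptoms split and cognition added). No pair of hypotheses gives nine: by constructs the pairs that include H1 give 11 to 13, and by instruments the three pairs give 15, 12 and 5. The documents state none of these as the basis.

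**4. What section 5 implies if followed as written.** With k independent tests at level a, the chance of at least one false positive when there is no effect is 1 − (1 − a)^k. For correlated tests, equicorrelated two-sided normal tests were integrated numerically. One test per outcome is assumed. The documents give no correlations, so a range is shown for a = .05:

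| Set | Independent | r = 0.3 | r = 0.5 | r = 0.7 |
|---|---|---|---|---|
| 11 H1 primary instruments | 1 − 0.95^11 = 43% | 37% | 30% | 22% |
| 7 H1 constructs | 1 − 0.95^7 = 30% | 27% | 23% | 18% |

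The expected number of false positives among the 11 is 11 × .05 = 0.55 at the section 5 level, against 11 × 0.00625 = 0.07 at the section 15 level.

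**The case against.** The best defence is that this is a pilot. Section 2 says the study will "preliminarily evaluate a technology-based information and coaching/support program", section 4 calls it a pilot, and section 15 drops its own calculation in the next sentence, so 0.00625 sizes nothing that is enrolled. That stands as far as the sample size goes. It does not settle how p-values will be read: section 2 predicts significant differences for all three hypotheses, the Instruments paragraph separates primary from secondary outcomes, and section 5 gives a significance rule without calling it exploratory.

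A second defence is that .05 could be the overall level, with 0.00625 as the per-test level derived from it. The two are compatible in principle, and for that reason the documents do not show that the sponsor has decided against correcting. But section 5 attaches .05 to every test and does not say that it is an overall level. The link is missing, and one sentence would supply it.

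Two stronger readings are tempting and should not be drawn:
- **That the sizing left out the primary hypothesis**, because H2 + H3 is the only pair of hypotheses giving eight. Hypothesis 1 alone also gives eight or nine, so the text does not support this.
- **That 0.00625 would itself fail to hold a family-wise .05 for nine outcomes.** By the same calculation the error is 5.5% if they are independent, 5.1% at r = 0.3, 4.4% at r = 0.5 and 3.4% at r = 0.7. Any excess is slight and disappears with moderate correlation.

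**Conclusion.** The point holds as an inconsistency that should be fixed before analysis. In section 15 the divisor, the outcome count and the number of hypotheses disagree, and the nine outcomes are not identified. Taken alone this is small: two more per group in a calculation that the plan does not use. The larger defect is that section 5 neither applies nor disclaims the correction. Read literally, it allows a chance of at least one false positive of 22% to 43% over the 11 primary instruments, or 18% to 30% over the seven constructs. These ranges rest on one test per outcome, no true effect, and assumed correlations from 0 to 0.7. None of this makes the trial invalid or bears on the choice of 60 participants.

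**What to change.** **Section 15.** List the outcomes in the corrected set, and make the divisor, the count and the number of hypotheses agree. If nine is right, the level is 0.05/9 = 0.00556 and the figure is 107 per group (t test, 0.5 SD). If eight is right, 0.00625 and 105 stand and the word nine must change.

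**Section 5.** State one rule that matches. A workable text: the listed Hypothesis 1 primary outcomes are tested with Holm's procedure at a family-wise two-sided .05; the tests for Hypotheses 2 and 3 are kept but reported as unadjusted and supportive, with 95% confidence intervals.

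**Alternative.** If all p-values are meant to be exploratory, say so in section 5, remove the multiplicity correction from section 15, and reword the predictions in section 2 so that they no longer promise statistical significance.

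While listing the outcomes, reconcile Hypothesis 1 with the IQCODE in the primary list. This may mean editing the Instruments paragraph as well as sections 2, 5 and 15.

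**Cost.** Text edits only, with no added participants, data or visits. Under the first option fewer results can be called significant; under the second none can be presented as confirmatory. Section 4 places the analysis after all data collection, so the rule can be fixed beforehand.
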